Statistical Analysis Plan for Social Anxiety MDMA-Assisted Therapy Investigation (SAMATI)

ID: IUSA5

Clinicaltrials.gov identifier: NCT05138068

Document date: August 8, 2022

Statistical Analysis Plan

Contents

SAMATI Statistical Analysis Plan	1
Study Design	2
Randomization Plan	2
Primary Outcome Measures	3
Leibowitz Social Anxiety Scale (LSAS)	3
Secondary Outcome Measures	3
Sheehan Disability Scale (SDS)	3
Internalized Shame Scale (ISS)	3
Acceptance of Shame and Embarrassment Scale (ASES)	3
Interpersonal Needs Questionnaire – Thwarted Belongingness Subscale (INQ)	3
Hidden Self Scale (HSS)	3
Self-Compassion Scale – Short Form (SCS)	4
Analytic plan	4
Primary Analyses	4
Secondary Analyses	4
Other Pre-registered Data Analyses	5

Study Design

This is a randomized, open-label delayed treatment study to assess the safety and effect of MDMAassisted therapy in treating 20 participants diagnosed with moderate-to-severe social anxiety disorder (SAD) of the generalized subtype. Half of the enrolled participants (N = 10) will proceed immediately into treatment once enrolled (immediate treatment group), and half (N = 10) will receive the experimental treatment after an initial 16 week wait (Delayed treatment group).

The primary outcome assessment will occur at two weeks post final integration session. There will also be a 6-month follow up assessment (28 weeks after final integration session). The study is preregistered at clinicaltrials.gov.

Randomization Plan

We will use permuted block randomization with random blocks of 2 and 4 to minimize the possibility of guessing. This randomization will be conducted by a PhD level scientist who is not involved in the trial so the study team can remain blinded.

Primary Outcome Measures

Leibowitz Social Anxiety Scale (LSAS)

The primary outcome assessed in the study is social anxiety symptom severity measured LSAS (Heimberg et al., 1999). The LSAS is a 24-item, semi-structured interview on the severity of social anxiety disorder, which assesses fear (0 to 3 = none, mild, moderate, severe) and avoidance (0 to 3 = never, occasionally, often, usually) of 24 social situations over the previous week, providing an overall social anxiety severity rating and subscale scores for performance fear, performance avoidance, social fear, and social avoidance. Scores range from a minimum of 0 to maximum of 144 with higher scores indicating a worse outcome.

Secondary Outcome Measures

Sheehan Disability Scale (SDS)

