The HSS (Levinson, Rodebaugh, Lim, & Fernandez, 2015) is a 4-item subscale of the Core Extrusion Schema–Revised and is thought to measure attempts to hide ones "true self" from others so as to avoid potential ostracism and rejection. This measure was created for use in SAD populations. The measure has demonstrated good psychometrics and the HSS subscale predicts the intensity of social interaction anxiety. This measure is included based on the idea that MDMA may increase participants' sense of authenticity and reduce fear of revealing vulnerable parts of oneself.

Self-Compassion Scale – Short Form (SCS)

The SCS short form (Raes, Pommier, Neff, & Van Gucht, 2010) is a 12-item self-report measure of selfcompassion, or responding to one's own failure, suffering or inadequacies with kindness and compassion and recognizing one's own flaws and suffering as part of common human experience. Because the measure is being administered repeatedly and we wanted it to be sensitive to change, we modified the measure slightly from to refer only to experiences in the last week. It is estimated to take about 3 minutes to complete. This brief measure has been shown to correlate highly with the well-validated longer version of this scale and to have excellent psychometric characteristics itself (Raes et al., 2010).

Analytic plan

Primary Analyses

Primary outcome analyses are intent-to-treat comparing mean scores on the LSAS at primary outcome assessment in the immediate treatment condition (n = 10) compared to the 16-week re-assessment in the delayed treatment condition (n = 10). A participant is considered eligible for the ITT analysis if they have completed at least one Experimental Session and at least one LSAS assessment beyond baseline. We will use an independent samples t-test to compare means across groups. Hedges' G will be reported as measure of effect size with confidence intervals calculated at 95%.

Secondary Analyses

Descriptive statistics for all primary and secondary outcome variables will be calculated.

To examine the change in social anxiety severity for all participants who received MDMA-assisted therapy, we will also collapse participants in the immediate and delayed treatment groups (N = 20) and use a paired samples t-test to compare mean change in LSAS scores from baseline to primary outcome.

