To examine sustained treatment effects over time for the entire sample (N=20), we use a paired sample ttest to compare LSAS mean scores at baseline with LSAS mean scores at 6-month follow up. Hedges' G will be used to estimate the effect size and confidence intervals will be calculated at 95%. If there is significant heterogeneity in variance across time points, Glass' Delta will be used to estimate the effect.

Secondary outcome analyses are intent-to-treat comparing mean scores on the measure (SDS, ASES, ISS, INQ, SCS, and HSS) at primary outcome assessment in the immediate treatment condition (n = 10) compared to the 16-week re-assessment in the delayed treatment condition (n = 10). We will use an independent samples t-test to compare means across groups. Hedges' G will be reported as measure of effect size with confidence interval calculated at 95%.

Change in secondary measures will be analyzed using the full sample by collapsing immediate and delayed treatment groups (N = 20) and conducting a series of paired samples t-tests comparing all secondary outcome measures (SDS, ASES, ISS, INQ, SCS, and HSS) at baseline, primary outcome and 6 month follow up.

We will report correlations between the primary outcome measure (LSAS) and secondary outcome measures. We will estimate the strength of the relation between change in social anxiety symptom

severity as measured by the LSAS and change in secondary outcome measures from baseline assessment to post-treatment. Specifically, we will subtract baseline scores from primary outcome scores for each measure and calculate bivariate correlations between this change score for the LSAS and change in each secondary outcome measure.

Other Pre-registered Data Analyses

Additional exploratory analyses not described here will be outlined in subsequent pre-registrations and posted to publicly available online repositories prior to data analysis.

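### The pooled follow-up analyses of the 20 participants are paired t-tests on complete pairs only; a repeated-measures model would use every recorded score and costs nothing if no visit is missed

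*SAP*

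**What the plan says.** All pooled before-after comparisons stand in the SAP under Analytic plan, Secondary Analyses.

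- LSAS, baseline to primary outcome: the two groups are combined (N = 20) to "use a paired samples t-test to compare mean change in LSAS scores from baseline to primary outcome".
- LSAS, baseline to 6 months: "To examine sustained treatment effects over time for the entire sample (N=20), we use a paired sample ttest to compare LSAS mean scores" at those two times.
- SDS, ASES, ISS, INQ, SCS and HSS: change is analysed "using the full sample by collapsing immediate and delayed treatment groups (N = 20) and conducting a series of paired samples t-tests", comparing scores "at baseline, primary outcome and 6 month follow up".

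The only analysis-set rule is under Primary Analyses and is written for the primary comparison. It admits a participant who has "completed at least one Experimental Session and at least one LSAS assessment beyond baseline". Under Study Design, the primary assessment is two weeks and the follow-up 28 weeks after the final integration session. The SAP names no imputation, repeated-measures model or sensitivity analysis for the pooled comparisons.

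**The concern.** The population named (the full or entire sample of 20) and the method named (a paired t-test) agree only if all 20 people have both scores in every comparison. The follow-up comes 28 - 2 = 26 weeks after the primary assessment, and one missed visit is 5% of the sample. The SAP's own entry rule can be met by someone with no 6-month score.

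Three things follow once a 6-month visit is missed:

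- The person leaves every contrast that uses that visit. Their score at the primary assessment, likely the best predictor of the missing value, is ignored.
- For one secondary measure, the contrasts among the three visits can rest on different people, so the mean changes need not add up.
- If those lost had responded less well, the completers' mean change is too favourable. The 6-month LSAS test is the one meant to show whether the effect is sustained, so this bears on the question it asks.

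**Working it through.** **The plan's own figure.** N = 20 is 10 + 10, the planned arm sizes. A paired t-test reaches it, with 19 df, only when all 20 pairs are complete. The SAP states no power, effect size, SD or dropout rate, so there is no derived figure to reproduce.

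**Precision, whatever the reason for loss.** In units of the SD of the change, the 95% CI half-width is t(0.975, n-1)/√n. The detectable effect is for 80% power at an assumed two-sided 0.05.

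| Complete pairs | df | CI half-width | Detectable effect |
|---|---|---|---|
| 20 | 19 | 0.47 | 0.66 |
| 18 | 17 | 0.50 | 0.70 |
| 16 | 15 | 0.53 | 0.75 |
| 14 | 13 | 0.58 | 0.81 |

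**Assumptions for the bias (none is in the SAP).** LSAS SDs are 18, 25 and 25 at baseline, primary outcome and 6 months. Correlations are 0.5 (baseline-primary), 0.45 (baseline-6 months) and 0.8 (primary-6 months). The true 6-month change is -25. The log-odds of missing the 6-month visit rise by 0.02, 0.04 or 0.08 per LSAS point at the primary assessment. Per SD of 25 points, the odds ratios are exp(0.5) = 1.6, exp(1) = 2.7 and exp(2) = 7.4.

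SD of the 6-month change = √(18² + 25² - 2 × 0.45 × 18 × 25) = √544 = 23.3. The standard error is 23.3/√20 = 5.2 with 20 pairs and 23.3/√16 = 5.8 with 16.

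**Simulated mean of the paired t-test, N = 20, true change -25:**

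| Slope per point | 10% loss | 20% loss | 30% loss | 95% CI coverage (%) |
|---|---|---|---|---|
| 0 (random) | -25 | -25 | -25 | nominal |
| 0.02 | -25.6 | -26.1 | -26.6 | 95 / 95 / 93 |
| 0.04 | -26.0 | -26.8 | -28.0 | 94 / 94 / 93 |
| 0.08 | -26.6 | -27.9 | -29.1 | 94 / 93 / 90 |

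At 20% loss the overstatement is 1.1, 1.8 and 2.9 points, or 0.2, 0.3 and 0.5 of the standard error of 5.8.

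**The alternative on the same data.** With only the 6-month score missing, the likelihood estimate regresses that score on the two earlier scores among completers, predicts it for all 20, and subtracts the mean baseline. It averages about -25.0 at slope 0.08 at all three loss rates.

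**Effect on significance.** With a true change of -10 and complete data, the noncentrality is 10/5.2 = 1.9 on 19 df, and about 44% of paired tests are significant. With 20% loss at slope 0.08 the paired mean is about -12.9 and about 56% are significant. With a true change of 0 and 20% loss, false rejection is about 5%, 6 to 7% and 7 to 8% at slopes 0.02, 0.04 and 0.08.

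**If loss depends on the unseen 6-month score.** At 20% loss the paired mean is about -29.4 and the likelihood estimate about -27.8, against -25. The model reduces this bias but does not remove it.

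**The case against.** The strongest reply is that nothing in the SAP shows that poorer responders will be lost. It gives no dropout figure and no reasons for loss, and a 26-week gap in an open-label study does not establish the direction. This stands. A reader might infer that the planned 6-month results will be biased towards benefit. The documents support only the conditional statement, and under weak or moderate selection the bias at 20% loss is 1 to 2 points against a standard error near 6.

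A reader might also infer that N = 20 is a false count of the pairs analysed. It is more naturally the planned sample size from Study Design, and the descriptive statistics planned for every outcome may well show the observed numbers. What remains is that the method cannot deliver the full sample once a visit is missed.

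The protocol is not shown and may hold a missing-data rule. The SAP prescribes no deletion, which is inferred from how the test works. But the point concerns the method that the SAP does fix, not a detail left to another document.

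Finally, these are uncontrolled secondary contrasts. With complete data the two methods agree, and under strong selection at 20% loss the model is no more precise (SD of the estimate about 5.6 for both). Its case there is the removal of bias, not precision.

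**Conclusion.** The point holds as a limitation of the chosen method. The pooled tests drop anyone without both scores and, at 6 months, discard information already collected. Loss unrelated to response costs precision only. Loss of poorer responders overstates the retained benefit, at 20% loss by roughly 1 to 3 LSAS points on a true change of -25. That range rests wholly on the assumed SDs, correlations, loss rate and selection slopes. The upper end needs an odds ratio of loss of about 7 per SD, which nothing in the SAP supports or rules out.

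The effect on significance should be judged against complete data: about 44% to 56% for a true change of -10 in the strong-selection case, a rise of some 12 percentage points. The primary comparison of the two groups is untouched. The change is worth making, chiefly because it costs so little.

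**What to change.** In Secondary Analyses, replace the pooled paired t-tests with one mixed model for repeated measures for each instrument (LSAS and the six secondary measures):

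- visit as a factor with three levels: baseline as the SAP defines it, primary outcome and 6 months;
- unstructured within-person covariance and Kenward-Roger degrees of freedom;
- every treated participant with any score included;
- visit contrasts reported with 95% CIs, and the number observed at each visit. For the 6-month LSAS contrast, base the planned standardised effect size on the model estimate.

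Add a short sensitivity analysis for loss that depends on the unseen 6-month score, for example by making the predicted scores of those missing worse by a range of fixed amounts. With 4 of 20 missing, a shift of d points moves the mean by 4/20 × d = 0.2d, so readers can see how large a shift would change the conclusion.

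The cost is revised wording and a few lines of code. With complete data the model gives the same mean change, standard error and 19 df as each paired t-test. With missing data it assumes that loss depends only on observed scores, which is weaker than what the completers' analysis needs.
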